**Treatment Groups and Duration:**

Study RHBW has 3 treatment groups during the 16-week Blinded Treatment Dosing Period: ixekizumab 80 mg Q4W, ixekizumab 80 mg Q2W, and placebo at 1:1:1 ratio. All patients randomized to an ixekizumab treatment group will receive a starting dose of ixekizumab 80 mg or 160 mg (1:1 ratio) at Week 0 followed by ixekizumab 80 mg Q4W or Q2W thereafter. All administrations are SC. Randomization will be stratified by country, baseline C-reactive protein (CRP) status (nonelevated or elevated, elevated defined as  $>5.00$  mg/L), and number of prior TNF inhibitors used (1 or 2). At Week 16, placebo patients will be rerandomized at a 1:1 ratio to ixekizumab 80 mg Q2W or Q4W. All patients will be on an ixekizumab regimen for the Extended Treatment Period (Weeks 16 to 52). The study duration will be up to 1 year for ixekizumab administration, and up to 1 year and approximately 4 months for study participation over 4 periods ([1] Screening Period: up to 42 days; [2] Blinded Treatment Dosing Period: 16 weeks; [3] Extended Treatment Period: 36 weeks; [4] Post-Treatment Follow-Up Period: at least 12 weeks after the date of the patient's early termination visit [ETV] or last regularly scheduled visit). Patients who complete Study RHBW may have the opportunity to continue into a long-term study instead of the Post-Treatment Follow-Up Period.

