### **8.2.1. Serious Adverse Events**

An SAE is any AE from this study that results in one of the following outcomes:

- death
- initial or prolonged inpatient hospitalization
- a life-threatening experience (that is, immediate risk of dying)
- persistent or significant disability/incapacity
- congenital anomaly/birth defect
- important medical events that may not be immediately life-threatening or result in death or hospitalization but may jeopardize the patient or may require intervention to prevent one of the other outcomes listed in the definition above.

If an SAE occurs after signing the ICF, but prior to receiving investigational product, it needs to be reported ONLY if it is considered reasonably possibly related to study procedure.

Study site personnel must alert Lilly or its designee of any SAE within 24 hours of investigator awareness of the event via a sponsor-approved method. If alerts are issued via telephone, they are to be immediately followed with official notification on study-specific SAE forms. This 24-hour notification requirement refers to the initial SAE information and all follow-up SAE information.

Pregnancy (during maternal or paternal exposure to investigational product) does not meet the definition of an AE. However, to fulfill regulatory requirements any pregnancy (during maternal or paternal exposure to investigational product) must be reported following the SAE process and data are to be collected on the outcome for both mother and fetus.

Investigators are not obligated to actively seek AEs or SAEs in subjects once they have discontinued and/or completed the study (the patient summary CRF has been completed). However, if the investigator learns of any SAE, including a death, at any time after a subject has been discharged from the study, and he/she considers the event reasonably possibly related to the study treatment or study participation, the investigator must promptly notify Lilly.

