#### **8.4.10.1.2. At Early Termination Visit**

For patients not enrolling in Study RHBW: If, at the last scheduled study visit, the patient's neutrophil count is  $< 1500$  cells/ $\mu\text{L}$  ( $< 1.50 \times 10^3/\mu\text{L}$  or  $< 1.50$  GI/L) and less than the patient's baseline neutrophil count, the following measures are to be taken:

- *Patients with Concurrent Infection:* If there is a concurrent infection that requires systemic anti-infective therapy, the patient is to receive appropriate medical care and a repeat test for neutrophil count is to be performed at least Q4W (or sooner as appropriate) until resolution of infection. Upon resolution of infection, the neutrophil count is to be monitored using the required study visits in Post-Treatment Follow-Up Period (Period 4): Visit 801 (4 weeks post-resolution of infection), Visit 802 (8 weeks

after Visit 801 unless otherwise specified), and Visit 803 (if necessary; 12 weeks after Visit 802); additional visits may be required depending on the degree of neutropenia. For patients with a neutrophil count below the abovementioned threshold at Week 52 who have already enrolled in Study RHBV, requirements for repeat test for neutrophil count will be specified in the Study RHBV protocol.

- *Patients without Concurrent Infection:* If there is no concurrent infection that requires systemic anti-infective therapy, the neutrophil count is to be monitored using the required study visits in the Post-Treatment Follow-Up Period (Period 4): Visit 801 (4 weeks post-ETV or last regularly scheduled visit), Visit 802, and Visit 803 (if necessary); additional visits may be required depending on the degree of neutropenia.

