#### **8.4.10.1.3. Post-Treatment Follow-Up Period**

For patients not enrolling in Study RHBV, at Visit 801 and subsequent visits, the following monitoring applies:

- As long as a patient's neutrophil count is  $<1000$  cells/ $\mu\text{L}$  ( $<1.00 \times 10^3/\mu\text{L}$  or  $<1.00$  GI/L) at any follow-up visit, the patient is to return for visits at least Q4W (may require unscheduled visits).
- As long as a patient's neutrophil count is  $\geq 1000$  cells/ $\mu\text{L}$  and  $<1500$  cells/ $\mu\text{L}$  ( $\geq 1.00 \times 10^3/\mu\text{L}$  and  $<1.50 \times 10^3/\mu\text{L}$  or  $\geq 1.00$  GI/L and  $<1.50$  GI/L) at any follow-up visit, the patient is to return for additional visit(s) at least every 4 to 8 weeks (may require unscheduled visits).
- If, at Visit 802 or Visit 803, the patient's neutrophil count is  $\geq 1500$  cells/ $\mu\text{L}$  ( $\geq 1.50 \times 10^3/\mu\text{L}$  or  $\geq 1.50$  GI/L) or greater than or equal to the patient's baseline neutrophil count (whichever is lower), the patient's participation in the study will be considered complete unless the investigator deems additional follow-up may be necessary.

If, at Visit 803, the patient's neutrophil count remains  $<1500$  cells/ $\mu\text{L}$  ( $<1.50 \times 10^3/\mu\text{L}$  or  $<1.50$  GI/L) and less than the patient's baseline neutrophil count, or if the investigator deems additional follow-up may be necessary, the investigator, in consultation with Lilly, or qualified designee, will determine the appropriate management of the patient and the appropriate timing of additional contact(s) or visit(s).

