## Schedule of Activities, Protocol I1F-MC-RHBW (Period 4)

	Post-Treatment Follow-Up for Patients Discontinuing Treatment at or After Week 16 (Period 4) y		
	Required Follow-Up Visits		As-Needed Follow-Up Visits
CRF V (visit) number	V801	V802	V803 and onwards
Study Weeks	LV + 4W	LV + 12W	LV + 24 W
Study Days	±14d	±14d	±14d
Concomitant medications	X	X	X
Vital signs (BP and pulse) d	X	X	X
Weight z	X	X	X
Preexisting conditions and medical history h	X	X	X
Adverse events	X	X	X
C-SSRS m	X	X	X
Self-Harm Supplement Form m	X	X	X
HBV		X r	
Serum chemistry	X	X	X
Hematology	X	X	X
Non-pharmacogenetic biomarker exploratory storage samples (urine, serum, plasma, RNA, and whole blood) u	X v	X v	
Immunogenicity testing w	X	X	
PK sampling w,x	X	X	

Schedule of Activities, Protocol I1F-MC-RHBW (Period 4)

Patients who discontinue treatment **prior** to Week 16 are to use the timetable below to schedule activities for Post-Treatment Follow-Up visits.

Discontinued Week No. (Visit No.)	Corresponding V801 (LV + 4 weeks)	Corresponding V802	Corresponding V803 (LV + 24 weeks)
Week 1 (Visit 3)	Week 5	Week 16	Week 25
Week 2 (Visit 4)	Week 6	Week 16	Week 26
Week 4 (Visit 5)	Week 8	Week 16	Week 28
Week 8 (Visit 6)	Week 12	Week 16	Week 32
Week 12 (Visit 7)	Week 16	Week 24	Week 36

	Post-Treatment Follow-Up for Patients Discontinuing Treatment Prior to Week 16 (Period 4) y		
	Required Follow-Up Visits		As-Needed Follow-Up Visits
	V801	V802	V803 and onwards
CRF (V) Visit Number	±14d	±14d	±14d
Study Days	±14d	±14d	±14d
Concomitant medications	X	X	X
Vital signs (BP and pulse) d	X	X	X
Weight z	X	X	X
Preexisting conditions and medical history h	X	X	X
Adverse events	X	X	X
C-SSRS m	X	X	X
Self-Harm Supplement Form m	X	X	X
HBV	X r	X r	
Serum chemistry	X	X	X
Hematology	X	X	X
Non-pharmacogenetic biomarker exploratory storage samples (urine, serum, plasma, RNA and whole blood) u	X v	X v	
Immunogenicity testing w	X	X	
PK sampling w,x	X	X	
Patient Global (Assessment of Disease Activity NRS)	X	X	
Spinal pain	X	X	
BASFI	X	X	
BASDAI	X	X	
CRP	X	X	

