- x PK samples are to be collected before IP injection.
- y Patients receiving IP who discontinue at any time prior to the end of the study or who complete the study (Week 52) and do not choose to enroll in Study RHBY, will have safety Follow-Up Visits 801 and 802 at 4 and 12 weeks, respectively, after the date of their last visit. Visit 803 will occur if a patient's neutrophil counts have not returned to the criteria defined in Section 8.4.10.1.
- z Weight is only captured on eCRF at V2, V8, V10, V15, and/or ETV. Body weight collected at other visits is used only for calculation of creatinine clearance.
- aa If not completed at Visit 2, the sample should be collected as soon as possible at the next scheduled visit.

---

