6.12.4.2. Neutrophil Follow-Up

Neutrophil counts will be followed throughout the study. Patients will continue in Period 4 until their neutrophil counts have recovered.

The neutrophil follow-up analysis will be conducted on the Neutrophil Follow-Up Population defined as patients who have an absolute neutrophil count < 1500 cells/ μL (SI units: $< 1.5 \times 10^9/\text{L}$) at the last scheduled visit or early termination visit before entering Period 4 and less than the patient's baseline absolute neutrophil count (that is, before first injection at Week 0). These patients are monitored during Period 4 until neutrophil recovery.

Neutrophil clinical recovery is defined as an absolute neutrophil count ≥ 1500 cells/ μL (SI units: $\geq 1.5 \times 10^9/\text{L}$) or greater than or equal to a patient's minimum absolute neutrophil count before first study drug injection at Week 0.

If a patient's neutrophil count has not recovered, within 12 weeks after entering the follow-up period (Visit 802), the patient will return for Visit 803 (12 weeks after Visit 802). Additional

visits may be required for appropriate patient management depending upon the degree of neutropenia. If at Visit 802, a patient has met the criteria for neutrophil recovery, the patient's participation in the study will be considered complete unless the investigator deems additional follow-up may be necessary.

The number and percentage of patients achieving neutrophil clinical recovery will be presented by treatment groups and week interval for the Neutrophil Follow-Up Population for Period 4. The number and percentage of patients with an absolute neutrophil cell count that is at least 25%, 50%, 75%, or 100% of the patient's baseline absolute neutrophil count (that is, before first injection at Week 0), irrespective of absolute neutrophil minimum, will be included in the summary.

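### For a patient who stops at Week 8, the follow-up timetable puts Visit 802 at 8 weeks after the last visit, while footnote y says 12 weeks and the synopsis at least 12, with no exception in either

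*Protocol*

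**What the plan says.** **Timetable.** The Period 4 schedule in Protocol Appendix 2 says that patients who discontinue prior "to Week 16 are to use the timetable below to schedule activities for Post-Treatment Follow-Up visits". The row for a stop at Week 8 (Visit 6) gives Visit 801 at Week 12, Visit 802 at Week 16 and Visit 803 at Week 32. All follow-up visits carry a window of ±14 days.

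**Footnote y.** This footnote is marked on the heading of the activities table for the same pre-Week-16 group. It covers patients who discontinue at any time before the end of the study, who "will have safety Follow-Up Visits 801 and 802 at 4 and 12 weeks, respectively, after the date of their last visit".

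**Synopsis.** Treatment Groups and Duration gives "Post-Treatment Follow-Up Period: at least 12 weeks after the date of the" early termination visit (ETV) or last regularly scheduled visit.

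**SAP Section 6.12.4.2.** For a neutrophil count that is still low, the rule is: "within 12 weeks after entering the follow-up period (Visit 802), the patient will return for Visit 803 (12 weeks after Visit 802").

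**Protocol Section 8.4.10.1.2.** For neutropenia with infection, Visit 802 comes 8 weeks "after Visit 801 unless otherwise specified), and Visit 803 (if necessary; 12 weeks after Visit 802").

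**Status of Visit 802.** Note c to Figure RHBW.1 requires Visits 801 and 802 of everyone; Visit 803 depends on neutrophil counts.

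**Reason for Week 16.** SAP Section 6.10.5.3 summarizes ASAS40 at 16 weeks after randomization for patients who stopped treatment early, so a follow-up visit is placed there.

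**The concern.** The timetable and footnote y both address patients who stop before Week 16, and for a Week 8 stop they give different dates for the last compulsory safety visit. The synopsis minimum agrees with footnote y and not with the timetable row.

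Visit 802 can close a patient's participation. Under Protocol Section 8.4.10.1.3, if the neutrophil count at that visit is at or above 1500 cells/µL or the patient's baseline (whichever is lower), "participation in the study will be considered complete unless the investigator deems additional follow-up may be necessary". After that, Section 8.2.1 applies: "Investigators are not obligated to actively seek AEs or SAEs in subjects once they have discontinued and/or completed the study". A site that follows the Week 8 row can therefore end active safety follow-up before the period that the synopsis describes.

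A second requirement touches the same visits. Protocol Section 8.4.10.2 and footnote r require HBV DNA monitoring 12 weeks after the last ixekizumab dose in patients who are positive for hepatitis B core antibody. The only tests scheduled after an early stop are at the ETV, Visit 801 and Visit 802.

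**Working it through.** **Inputs.** Visit weeks come from the pre-Week-16 timetable in Appendix 2. The 12-week figures come from footnote y and the synopsis.

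**Check on the last visit.** The timetable labels Visit 801 as last visit + 4 weeks and Visit 803 as last visit + 24 weeks. In the Week 8 row, 12 − 4 = 8 and 32 − 24 = 8, so the timetable itself takes Week 8 as the last visit. The same two labels reproduce in all five rows.

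**Interval to Visit 802** = Visit 802 week − last-visit week. The window adds ±2 weeks.

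| Stop (last visit) | Visit 801 | Visit 802 | Last visit to 802 | With window | 801 to 802 |
|---|---|---|---|---|---|
| Week 1 | 5 | 16 | 16 − 1 = 15 | 13 to 17 | 11 |
| Week 2 | 6 | 16 | 16 − 2 = 14 | 12 to 16 | 10 |
| Week 4 | 8 | 16 | 16 − 4 = 12 | 10 to 14 | 8 |
| Week 8 | 12 | 16 | 16 − 8 = **8** | 6 to 10 | 4 |
| Week 12 | 16 | 24 | 24 − 12 = 12 | 10 to 14 | 8 |

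**Against footnote y.** 12 weeks ±14 days is 10 to 14 weeks. The scheduled dates for Week 1 (15, above) and Week 8 (8, below) lie outside; Week 2 (14) is at the edge and inside.

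**Against the synopsis.** Only Week 8 is short of 12 weeks, by 12 − 8 = 4 weeks. Its latest permitted date, 10 weeks, still does not reach 12. Footnote y applied to a Week 8 last visit would give 8 + 12 = Week 20, against Week 16 in the row. This shows the size of the gap only.

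**Against SAP Section 6.12.4.2.** The SAP puts Visit 803 at 12 weeks after Visit 802, and the timetable labels Visit 803 as last visit + 24 weeks. Together these put Visit 802 at 24 − 12 = 12 weeks. In the Week 8 row the gap from 802 to 803 is 32 − 16 = 16 weeks.

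**HBV tests for a Week 8 stop.** Tests fall at Weeks 8, 12 and 16. The documents do not fix the last dose date, so three are assumed:

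| Last ixekizumab dose (assumed) | Tests, weeks after dose | Last test with ±2 weeks |
|---|---|---|
| Week 4 | 4, 8, 12 | 10 to 14 |
| Week 6 | 2, 6, 10 | 8 to 12 |
| Week 8 | 0, 4, 8 | 6 to 10 |

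On scheduled dates, the 12-week test is met only for a Week 4 dose. A Week 6 dose can reach 12 weeks at the end of the window; a Week 8 dose cannot.

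**The case against.** The strongest reply is that the timetable is the specific rule and the other texts are general. It is an explicit instruction to this group, and Protocol Sections 7 and 7.1.1.1 send early discontinuers to Appendix 2. Its Visit 802 column, unlike those for 801 and 803, carries no offset from the last visit. The Week 16 anchor is also deliberate. All of that stands as an account of how the row arose. But no passage says that the timetable overrides footnote y or the synopsis, and if it does, those two are wrong for this group and need the exception written in. Nor does the anchor by itself force a shorter follow-up: the Week 4 and Week 12 rows have a visit at Week 16 and still reach 12 weeks.

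The supporting texts are weaker than the core. The SAP sentence can be read loosely, since 8 weeks is within 12, although its spacing to Visit 803 points to 12. Section 8.4.10.1.2 allows another spacing in its own words and counts Visit 801 from resolution of infection, so it is not a contradiction. The HBV shortfall depends on assumed dose dates, and a dose taken on the day of an ETV at Week 8 is the least likely of the three.

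The consequence is also limited by safeguards:
- The schedule is a minimum frequency (Protocol Section 4.1).
- Adverse events that caused discontinuation are followed to resolution or stabilization (Section 8.2).
- Serious events thought related must be reported whenever the investigator learns of them (Section 8.2.1).
- With a neutrophil count from 1000 to below 1500 cells/µL, "the patient is to return for additional visit(s) at least every 4 to 8 weeks (may require unscheduled visits"); below 1000, visits are at least every 4 weeks.

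These reduce the consequence and leave the contradiction in place.

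**Conclusion.** The concern holds, as a minor point. For a stop at Week 8, the timetable places the last compulsory follow-up visit 8 weeks after the last visit (6 to 10 with the window), against 12 weeks in footnote y and at least 12 in the synopsis. It is the only one of five rows below the synopsis minimum. The result assumes that the ETV is held in the discontinuation week, which the timetable's own labels imply. The HBV part is conditional on dose dates and is not needed for the conclusion.

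No test, estimand or comparative analysis is affected; Period 4 safety is summarized descriptively. The documents do not say how many patients would stop at Week 8.

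**What to change.** Reconcile the Week 8 timetable row with footnote y and the synopsis. In the same edit, align Protocol Section 8.4.10.1.2, Section 8.4.10.2 with footnote r, and SAP Section 6.12.4.2. Keep the Week 16 post-discontinuation assessment that SAP Section 6.10.5.3 uses. Which passage governs is for the sponsor to decide; this review does not propose a schedule.

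The cost is text only: one timetable row or footnotes y and r, one synopsis line, two protocol sections and one SAP sentence. Whether any visit date changes depends on the passage chosen.

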## Schedule of Activities, Protocol I1F-MC-RHBW

Abbreviations: ASAS HI = ASAS Health Index; BASDAI = Bath Ankylosing Spondylitis Disease Activity Index; BASFI = Bath Ankylosing Spondylitis Functional Index; BASMI = Bath Ankylosing Spondylitis Metrology Index; BP = blood pressure; CRF = case report form; CRP = high sensitivity C-reactive protein; C-SSRS = Columbia–Suicide Severity Rating Scale; d = days; DNA = deoxyribonucleic acid; ECG = electrocardiogram; EQ-5D-5L = European Quality of Life–5 Dimensions–5 Level; ETV = early termination visit; FSH = follicle stimulating hormone; HBcAb+ = positive for anti-hepatitis B core antibody; HBsAb = anti-hepatitis B surface antibody; HBV = hepatitis B virus; HCV = hepatitis C virus; HIV = human immunodeficiency virus; HLA = human leukocyte antigen; INR = international normalized ratio; IP = investigational product; JSEQ = Jenkins Sleep Evaluation Questionnaire; LV = last visit; MASES = Maastricht Ankylosing Spondylitis Enthesitis Score; NRS = numeric rating scale; NSAID = nonsteroidal anti-inflammatory drug; PK = pharmacokinetic; PPD = purified protein derivative; PT = prothrombin time; PTT = partial thromboplastin time; QIDS-SR16 = Quick Inventory of Depressive Symptomatology–Self-Report (16 Items); rad-axSpA = radiographic axial spondyloarthritis; RNA = ribonucleic acid; SDAL = Study Drug Administration Log; SF-36 = Short Form 36; SIJ = sacroiliac joints; SJC = swollen joint count; SpA = spondyloarthritis; SPARCC = Spondyloarthritis Research Consortium of Canada; T4 = thyroxine; TB = tuberculosis; TJC = tender joint count; TSH = thyroid stimulating hormone; V = study visit; W = study week; WPAI-SpA = Work Productivity Activity Impairment Questionnaire–Spondyloarthritis.

- a If a patient who has received at least 1 dose of IP discontinues from study treatment early, the patient will complete the ETV and then enter the Post-Treatment Follow-Up Period (Period 4). If a patient discontinues prior to Week 16, the patient will complete additional activities during Period 4.
- b Demographics includes recording of year of birth, gender, race, and ethnicity.
- c One complete physical examination (excluding pelvic, rectal examination) will be performed at screening. All physical examinations throughout the study must include a symptom-directed physical as well as examination of heart, lungs, abdomen, eyes, and visual examination of the skin.
- d BP and pulse will always be measured in sitting position and will be recorded before IP dosing at all visits; in addition, BP and pulse will be recorded approximately 1 hour post-dosing at baseline (Week 0) and Week 16. Refer to Section 8.4.2 for more details.
- e Habits include recording of caffeine, alcohol, and tobacco consumption.
- f A posterior anterior chest x-ray will be taken locally at screening unless one has been obtained within 6 months of screening (Visit 1) (provided the x-ray and/or report are available for review). Refer to Section 8.4.6 for more details.
- g Refer to rescreening guidance as appropriate (Section 5.3).
- h Evaluation includes historical events and preexisting conditions.
- i Patients need to be asked about presence of eye symptoms; if eye symptoms are present, then an eye examination is required. Refer to Section 8.4.5 for specific instructions.
- j Refer to Section 6.1.1 for specific IP administration instructions.
- k An x-ray of the SIJ will be performed during the Screening Period (Period 1) unless an x-ray taken prior to screening is available for central reading, is of good quality, and confirms diagnosis of rad-ax-SpA. All x-rays require central reading ONLY, regardless of date taken. Central reading will define eligibility using the modified New York (mNY) criteria. If central reading of a preexisting x-ray is not consistent with rad-ax-SpA by central reading, a new x-ray of the SIJ may be taken during Period 1 and sent in for central reading.
- l Cervical and lumbar spine only; serves: 1) as baseline for later assessments of structural changes and 2) to evaluate presence of total ankylosis at screening (refer to Section 5.2, Exclusion Criterion [11]). X-ray of the spine does not need to be repeated if one is available that was taken  $\leq 3$  months prior to screening and has passed quality assessment by central reading vendor.

- m A Self-Harm Follow-Up Form is to be completed for each discrete self-harm event identified on the C-SSRS and the Self-Harm Supplement Form.
- n HLA-B27 test will be performed centrally.
- o Approval from the Lilly clinical research physician or clinical research scientist must be obtained before a CRP retest is permitted. If the CRP lab is retested, the most recent value will be used for randomization.
- p In countries where the QuantiFERON®-TB Gold test or T-SPOT® is available, either test may be used instead of the PPD TB test. The QuantiFERON®-TB Gold test may be performed locally or centrally; the T-SPOT® must be performed locally. PPD tests must be read 2-3 days after Visit 1. Refer to Section 8.4.6 for more details.
- q For female patients  $\geq 40$  and  $< 60$  years of age who have had a cessation of menses for at least 12 months, an FSH test will be performed to confirm nonchildbearing potential (FSH  $\geq 40$  mIU/mL or  $\geq 40$  IU/L). FSH test will be performed centrally.
- r All patients will be tested for HBV at screening. Patients that are HBcAb+ at screening, regardless of HBsAb status, will have a serum HBV DNA obtained by the central laboratory. Patients that are found to be HBV DNA positive (detectable) at screening will be excluded from the trial. Patients that are HBV DNA negative (undetectable) may be enrolled into the study with required HBV DNA monitoring every 3 months during treatment and 12 weeks after the last dose of ixekizumab. If the result of the HBV DNA testing is positive, the patient is to be discontinued from the study and is to receive appropriate follow-up medical care (refer to Section 8.4.10.2 for further information regarding the timing of discontinuation).
- s Only for females of childbearing potential. Serum pregnancy test will be done at Visit 1 only and will be performed centrally. Patients determined to be pregnant will be discontinued from treatment and will no longer be administered IP (see Section 7.1). Patients will undergo urine pregnancy testing at the clinic during scheduled visits through Week 52. Additional urine pregnancy testing can be performed at the investigator's discretion. If required per local regulations, testing can occur at other intervals during the study treatment period and/or follow-up period.
- t For the fasting lipid profile, patients are not to eat or drink anything except water for 12 hours prior to test.
- u Where collection is allowed by local regulations.
- v Only serum and plasma are collected at this visit.
- w Immunogenicity samples may also be analyzed for ixekizumab serum concentration to facilitate in the interpretation of immunogenicity data. An additional blood sample will be collected, when possible, for any patient who experiences a potential systemic allergic/hypersensitivity reaction during the study as judged by the investigator.
- x PK samples are to be collected before IP injection.
- y Patients receiving IP who discontinue at any time prior to the end of the study or who complete the study (Week 52) and do not choose to enroll in Study RHBY, will have safety Follow-Up Visits 801 and 802 at 4 and 12 weeks, respectively, after the date of their last visit. Visit 803 will occur if a patient's neutrophil counts have not returned to the criteria defined in Section 8.4.10.1.
- z Weight is only captured on eCRF at V2, V8, V10, V15, and/or ETV. Body weight collected at other visits is used only for calculation of creatinine clearance.
- aa If not completed at Visit 2, the sample should be collected as soon as possible at the next scheduled visit.

---

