## 7. Discontinuation Criteria

The reason for and date of discontinuation from study treatment (investigational product) and reason for and date of discontinuation from study participation will be collected for all randomized patients.

For any patient permanently discontinuing from study treatment, the investigational product will be withheld, and the patient will complete the ETV and the Post-Treatment Follow-Up Period (Period 4), as shown in the Schedule of Activities ([Appendix 2](#)). For patients discontinuing prior to Week 16, the patient will complete additional assessments as described in Section 7.1.1.1 and shown in the Schedule of Activities ([Appendix 2](#)).

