#### **8.4.10.2. Hepatitis B Monitoring**

Patients that are HBcAb+ at screening, regardless of other hepatitis B testing results, will have a serum HBV DNA specimen obtained to be analyzed by the central laboratory. Such patients that are determined to be HBV DNA negative (undetectable) may be enrolled into the study with required HBV DNA monitoring every 3 to 4 months during treatment and 12 weeks after the last dose of ixekizumab. Patients that are found to be HBV DNA positive (detectable) at screening will be excluded from the trial.

If the result of any subsequent HBV DNA testing is positive, the patient is to be discontinued from the study treatment, is to continue safety follow up, and is to receive appropriate follow-up medical care, including consideration for antiviral therapy. A specialist physician in the care of patients with hepatitis (for example, infectious disease or hepatologist subspecialists) is to be

consulted and potentially start antiviral therapy prior to discontinuation of any immunosuppressant or immunomodulatory therapy (including investigational drug). Timing of discontinuation from the study and of any immunosuppressant/immunomodulatory therapy (including investigational product) needs to be based on the recommendations of the consulting specialist physician in conjunction with the investigator and medical guidelines/standard of care.

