6.10.5.3. Analysis Including Efficacy Data Post Treatment Discontinuation

Per recommendation in the 2010 National Research Council report *The Prevention and Treatment of Missing Data in Clinical Trials*, additional efficacy data for patients who prematurely discontinued Period 2 are collected during the Post-Treatment Follow-Up Period (Period 4). Patients who discontinue treatment before Week 16 are instructed to schedule a Post-Treatment Follow-Up visit such that the post-treatment data will be collected 16 weeks after initial randomization. The efficacy data of ASAS40 at Week 16 will be summarized by treatment group, but no formal statistical comparison will be performed.

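### For patients who stop treatment at Week 8, the early-discontinuation timetable ends required safety follow-up 8 weeks after the last visit, although the same schedule's footnote and the synopsis require 12.

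*Protocol*

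**What the plan says.** Three places in the protocol set the length of post-treatment follow-up.

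- **Synopsis, Treatment Groups and Duration.** Period 4 is described as "Post-Treatment Follow-Up Period: at least 12 weeks after the date of the" early termination visit or last regularly scheduled visit.
- **Appendix 2, footnote y.** Patients on investigational product who discontinue at any time before the end of the study "will have safety Follow-Up Visits 801 and 802 at 4 and 12 weeks, respectively, after the date of their last visit". The marker for this footnote sits on the heading of the early-discontinuation schedule itself.
- **Appendix 2, Period 4 timetable.** Patients who stop before Week 16 "are to use the timetable below to schedule activities for Post-Treatment Follow-Up visits". The row at issue reads "Week 8 (Visit 6) Week 12 Week 16 Week 32", the columns being time of stopping, V801, V802 and V803.

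The footnotes to Figure RHBW.1 make V801 and V802 mandatory for everyone and V803 conditional on neutrophil counts.

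SAP Section 6.10.5.3 explains the interest in Week 16: early stoppers are told to "schedule a Post-Treatment Follow-Up visit such that the post-treatment data will be collected 16 weeks after initial randomization". Protocol Section 8.4.10.2 separately asks, for patients positive for hepatitis B core antibody, for "required HBV DNA monitoring every 3 to 4 months during treatment and 12 weeks after the last dose of ixekizumab".

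**The concern.** A site with a Week 8 stopper cannot follow both the row and the footnote at their nominal dates. If it follows the row, as instructed, the last mandatory visit comes 4 weeks short. Required collection of adverse events, C-SSRS, laboratory, immunogenicity and PK data stops there, in any arm.

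Protocol Section 8.2 still requires serious, otherwise medically important, related or treatment-ending events that are already known to be followed to resolution or stability. What is lost is detection of new events and new abnormal results in the last 4 weeks. Section 8.2.1 does not oblige investigators to look for events once a patient has finished the study.

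Hepatitis B monitoring is a smaller part of the same problem. For some core-antibody-positive patients the last scheduled HBV DNA test comes less than 12 weeks after the last active dose, and V803 has no HBV entry to make up for it.

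**Working it through.** **Inputs.** Visit weeks come from the Appendix 2 timetable, the ±14-day window from the early-discontinuation schedule, the 12-week rules from footnote y, the synopsis and Section 8.4.10.2, and the dosing weeks from Table RHBW.2. LV is the last visit, taken as the week of stopping.

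**Step 1: confirm the anchor.** The timetable labels V801 as LV + 4 weeks and V803 as LV + 24 weeks. Both hold in every row (for Week 8: 12 − 8 = 4 and 32 − 8 = 24), so LV is Week 8 in the row at issue.

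**Step 2: weeks from LV to V802, by row.**

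| Stop (LV) | V801 | V802 | V802 − LV | With ±2 weeks | LV + 12 |
|---|---|---|---|---|---|
| Week 1 | 5 | 16 | 15 | 13 to 17 | 13 |
| Week 2 | 6 | 16 | 14 | 12 to 16 | 14 |
| Week 4 | 8 | 16 | 12 | 10 to 14 | 16 |
| **Week 8** | **12** | **16** | **8** | **6 to 10** | **20** |
| Week 12 | 16 | 24 | 12 | 10 to 14 | 24 |

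Only the Week 8 row falls below 12 weeks at its nominal date, by 12 − 8 = 4 weeks.

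**Step 3: can the windows reconcile the two rules?** The timetable gives Week 16 ± 2, that is Weeks 14 to 18. Footnote y gives Week 20 ± 2, that is Weeks 18 to 22. They share only Week 18, which is 18 − 8 = 10 weeks after LV and still under the synopsis minimum.

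**Step 4: HBV DNA timing.** Core-antibody-positive patients who stop at Week 8 have scheduled tests at the early termination visit, Week 12 and Week 16. Weeks from the last ixekizumab dose to the Week 16 test are:

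- Q2W, last dosed at Week 6: 16 − 6 = 10, short of 12. Twelve weeks is reached at Week 18, the end of the window.
- Either regimen, if the Week 8 dose was taken: 16 − 8 = 8, short of 12. This is less likely, because Section 7 says "For any patient permanently discontinuing from study treatment, the investigational product will be withheld".
- Q4W, last active dose at Week 4: 16 − 4 = 12, rule met.
- Placebo: no ixekizumab dose to count from.

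**Step 5: number of patients.** The documents give neither stop rates nor core-antibody prevalence, so these are assumptions.

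- 2% to 5% stop at about Week 8: 300 × 0.02 = 6 to 300 × 0.05 = 15 patients, or 2 to 5 per arm at 1:1:1.
- 5% to 10% are core-antibody positive. If only Q2W patients miss the timing: 2 × 0.05 = 0.1 to 5 × 0.10 = 0.5 patients. If both active arms were dosed at Week 8: 4 × 0.05 = 0.2 to 10 × 0.10 = 1.0 patients.

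**The case against.** The strongest reply is that Week 16 is deliberate. The V802 column carries no offset label, the first four rows all read Week 16, and the SAP says why. The Week 1 and Week 2 rows also depart from footnote y, so the timetable can be read as a specific schedule that overrides a general footnote. This explains the date but does not remove the conflict. The Week 1 and Week 2 departures lengthen follow-up and so respect the synopsis minimum, whereas the Week 8 row breaks it. The SAP's reason concerns efficacy data only, and no text exempts these patients from 12 weeks of safety follow-up.

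A second reply is that the ordinary window already lets anyone attend at 10 weeks, so a Week 18 visit would satisfy both rules. That is true of the windows, but it makes the last permitted day of one schedule the first permitted day of the other. A site that keeps to the nominal date ends at 8 weeks.

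A third is that Section 8.4.10.2 and footnote r impose the HBV test regardless of the timetable, and that Section 4.1 makes the schedule a minimum monitoring frequency. This stands in part: the duty remains, but no scheduled visit delivers it for the affected Q2W patients.

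Two supporting points carry little weight. The 8-week spacing in Section 8.4.10.1.2 ("after Visit 801 unless otherwise specified), and Visit 803 (if necessary; 12 weeks after Visit 802") concerns neutropenic patients with a concurrent infection and allows for exceptions. The Week 12 row meets both aims only because its V801 happens to fall at Week 16. In the Week 8 row V801 falls at Week 12, so two visits cannot provide LV + 4, Week 16 and LV + 12.

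**Conclusion.** The plan is wrong as written on this point. The timetable row contradicts the footnote attached to it and the synopsis minimum, and the calendar arithmetic leaves no doubt: 8 weeks against 12.

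The consequence is small. It affects patients who stop at about Week 8, 6 to 15 of 300 under the assumed 2% to 5% stop rate, and costs each about 4 weeks of active safety surveillance. The HBV shortfall is at most about one patient under the further assumption of 5% to 10% core-antibody positivity. The primary and secondary efficacy analyses are untouched. It is a minor correction, worth making at the next amendment.

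**What to change.** In the Week 8 row, keep Week 16 as an efficacy visit and set V802 at Week 20 (LV + 12 weeks), with HBV DNA where applicable and the other V802 safety assessments.

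Stops between scheduled visits have no row. One sentence saying that V802 is then never earlier than 12 weeks after the last visit would settle that. It largely repeats footnote y, so it is a clarification.

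The text change is one timetable row and one sentence. Because the row then has three required visits, the Week 16 efficacy visit also needs its own label and entry in the activity table. The operational cost is one extra visit per patient who stops at about Week 8, or 6 to 15 visits under the assumed rates.
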